## 4. ANALYSIS POPULATIONS

### *Safety Analysis Set*

The Safety Analysis Set comprises all patients who receive at least 1 dose of the study treatment or component of the study treatment.

### *Efficacy-Evaluable Analysis Set*

The Efficacy-Evaluable Analysis Set comprises all patients who receive at least 1 dose of the study treatment or component of the study treatment and have a post baseline response assessment per iRECIST at Week 12. Subjects who discontinued prior to Week 12 due to radiological disease progression will be included. Subjects who do not have a post baseline response assessment conducted will not be included in the analysis of efficacy.

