Efficacy-Evaluable Analysis Set:

The primary efficacy analysis will be based on the Efficacy-Evaluable Analysis Set, which comprises all patients who receive at least 1 dose of the study treatment or component of the study treatment and have a post baseline response assessment per iRECIST at Week 12. Patients who discontinued treatment prior to Week 12 due to disease progression will be included. Patients who do not have a post baseline response assessment conducted will not be included in the analysis of efficacy.

Safety Run-In Set:

All patients who receive at least 1 dose of the study treatment or component of the study treatment apart of the safety run-in.

Immunologic Analysis Set:

All patients who receive at least 1 dose of the study treatment or component of the study treatment and have at least one valid post-baseline immunologic assessment available.

General Methods:

All summarizations will be presented separately for each cohort, and over all subjects combined.

For continuous variables, descriptive statistics (number (n), mean, median, standard deviation, minimum and maximum) will be presented. For categorical variables, frequencies and percentages will be presented. For time-to-event variables, percentages of patients experiencing that event will be presented and median time-to-event will be estimated using the Kaplan-Meier method. As appropriate, a 95% CI will be presented. Graphical displays will be presented, as appropriate. All data collected will be presented in by-patient data listings.

Patients demographic characteristics including age, gender, and race will be analyzed, with categorical variables summarized in frequency tables while continuous variables summarized using mean (standard deviation) and median (range).

Safety evaluations will be based on the incidence, severity, attribution and type of AEs, and changes in the patient's vital signs, and clinical laboratory results. Summarization of toxicity data will focus on incidence of any serious adverse events, adverse events, drug-related adverse events, and adverse events

leading to discontinuation or death, and will be presented in tabular form by system organ class and preferred term. Adverse events will be assessed for severity according to the NCI CTCAE, version 5.0.

Objective response rate (ORR) is defined as the proportion of patients with a confirmed best response of CR or PR by iRECIST.

Inclusion Criteria:

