8.2 Participant Discontinuation/Withdrawal from the Study

The patients may withdraw from study treatment if they decide to do so, at any time and irrespective of the reason. In addition, the Investigator or the Sponsor has the right to withdraw the patient from the study and/or stop the study at any time. All efforts should be made to document the reason for discontinuation, and this should be documented in the electronic case report form (eCRF).

Other criteria for possible discontinuation are:

- Disease progression
- Unacceptable toxicity as judged by the Principal Investigator
- Adverse events which are dose-limiting toxicities
- Withdrawal of consent
- Subject is lost to follow-up
- Subject non-compliance
- Use of another non-protocol anti-cancer treatment
- Pregnancy
- Completed 24 months of study treatment

Withdrawn patients will be followed according to the study procedures as specified in this protocol.

The patients may withdraw from the study follow-up period, before study completion if they decide to do so, at any time and irrespective of the reason. The reason for withdrawal from the study treatment or study follow-up will be documented in the eCRF.

A patient who receives at least one study treatment and who discontinues from the trial for any reasons will not be replaced except for patients that withdraw for reasons other than toxicity during the safety run-in phase of the study.

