10.3 Populations for Analyses

The following analysis populations will be used for presentation of the data:

Safety Analysis Set: The safety analysis will be based on the Safety Analysis Set, which comprises all patients who receive at least 1 dose of the study treatment or component of the study treatment.

Efficacy-Evaluable Analysis Set: All patients who receive at least 1 dose of the study treatment or component of the study treatment and have a post baseline response assessment per iRECIST at Week 12. Patients who discontinued prior to Week 12 due to disease clinical progression will be included. Patients who do not have a post baseline response assessment conducted will not be included.

Safety Run-In Set: All patients who receive at least 1 dose of the study treatment or component of the study treatment apart of the safety run-in.

Immunologic Analysis Set: All patients who receive at least 1 dose of the study treatment or component of the study treatment and have at least one valid post-baseline immunologic assessment available.

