# 7. EFFICACY ANALYSIS

## 7.1 Primary Efficacy Analysis

The primary efficacy analysis will be based on the Efficacy-Evaluable Analysis Set at week 12. All efficacy variables will be presented by cohort. The following primary efficacy variables will be summarized to determine the anti-tumor activity of SNS-301:

Objective Response Rate (ORR)

- ORR is defined as the proportion of patients with a confirmed best response of iCR or iPR by iRECIST.
- ORR, and 90% CI at week 12 based on the exact binomial distribution will be presented, including number and percent of patients in each overall response category.

Sponsor: Sensi Biotherapeutics

Protocol: SNS301-2-2

- Best Overall Response ( BOR) will also be presented.

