## 9. STATISTICAL/ANALYTICAL ISSUES

### 9.1 Handling of Dropouts or Missing Data

All available data will be presented on the data listings as collected.

Algorithms for imputing partial or missing dates related to AEs and prior/concomitant medications are shown below.

Table 3      Imputation Rules for Partially Missing Dates

Variable	Missing Day	Missing Day, Month	Missing Day, Month, Year
Date of Last Therapy/Date of Initial Diagnosis	Assign 1	Assign January 1 if prior to date of informed consent, otherwise use date of informed consent	Missing (do not impute)
Adverse Event/Medication Start Date	Assign first day of month unless it is the month of first dose of study medication. Otherwise, assign date of first dose of study medication.	Assign January 1 unless the year is year of first dose of study medication Otherwise, assign date of first dose of study medication.	Assign date first dose of study medication.
Adverse Event/Medication End Date	Assign the last day of the month or end of study date, whichever is earlier.	Assign December 31 or end of study date, whichever is earlier.	If ongoing, end date is missing. Otherwise, assign end of study date.

Every effort to re-contact the patient lost to follow-up patients will be made, to identify the reason why he/she failed to attend the visit, and to determine his/her health status, including at least his/her vital status. Data from lost to follow-up subjects to the date of last recorded contact will be included in the analyses.

Non-evaluable patients will be replaced.

Sponsor: Sensi Biotherapeutics

Protocol: SNS301-2-2

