## 9.5 Interim Analysis and Data Monitoring

A Safety Committee will be formed to monitor safety on a periodic basis. The Safety Committee will meet at the completion of the safety run-in to review safety data collected from the point of first patient in (FPI) to review safety, or as needed. The safety data will include demographic data, adverse events, serious adverse events, and relevant laboratory data.

The interim efficacy assessment, for each cohort, will occur after 15 patients were enrolled and completed the 12-week follow-up period. The objective response rate, for each cohort, will be assessed at the completion of stage 1 of the 2-stage design, after 15 patients complete the 12-week follow-up period or discontinue prior due to disease progression. A safety review will occur in parallel to the efficacy assessment of the first 15 patients in each cohort.

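### The SAP narrows the primary ORR set to early stoppers with radiological progression, against the protocol and without saying so, which raises the reported ORR and, if those patients are replaced, the type I error

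*SAP*

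**What the plan says.** The primary ORR rests on one set. SAP 7.1: "The primary efficacy analysis will be based on the Efficacy-Evaluable Analysis Set at week 12". The same set defines the 15 evaluable patients per cohort at stage 1 (Protocol 5.2, SAP 2.2).

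Who enters that set after stopping early is worded differently from place to place:

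- SAP 4: "Subjects who discontinued prior to Week 12 due to radiological disease progression will be included".
- Protocol 10.3: "Patients who discontinued prior to Week 12 due to disease clinical progression will be included".
- Protocol synopsis: "Patients who discontinued treatment prior to Week 12 due to disease progression will be included".
- SAP 9.5, on when the stage 1 look takes place: "after 15 patients complete the 12-week follow-up period or discontinue prior due to disease progression".

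SAP 1 says the SAP sets out where its methods depart from the protocol. It names no departure here.

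A further sentence appears, with minor variation, in Protocol 10.3, the synopsis and SAP 4: "Patients who do not have a post baseline response assessment conducted will not be included".

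On replacement, SAP 9.1 states "Non-evaluable patients will be replaced", as do Protocol 5.2 and SAP 2.2. Protocol 8.2 says the opposite for treated patients: "A patient who receives at least one study treatment and who discontinues from the trial for any reasons will not be replaced", with an exception only for the safety run-in.

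SAP 2.4 adds, for Cohort A only, that patients who have progressed or are unevaluable at 12 weeks do not count in the futility assessment.

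**The concern.** A patient who deteriorates clinically and stops before Week 12 is almost always a non-responder, because a confirmed response needs a repeat scan at least 4 weeks after the first (Protocol 9.1.1). Whether that patient stays in the denominator should not depend on which document the programmer follows, or on whether a scan happened to be taken. SAP 7.1 counts drop-outs as non-responders for DCR but has no such rule for ORR.

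The eligibility criteria make such patients foreseeable: the minimum life expectancy is 3 months, close to the Week 12 landmark, and Cohort A admits patients with first evidence of progression on a checkpoint inhibitor. For clinically unstable patients, Protocol Table 3 leaves the repeat scan to the physician's discretion. The trial is open-label with investigator-read response, so a rule left open could be chosen once responses are known, when one patient can decide 4/30 or 7/30.

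**Working it through.** **1. Which patients are affected**

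| Patient who stops before Week 12 | Protocol 10.3 | SAP 4 |
|---|---|---|
| Non-progressing Week 6 scan, then clinical progression with no progression scan | In | Out |
| Clinical progression before any post-baseline scan | Included by one sentence, removed by the next | Out |

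The SAP's change of wording therefore acts mainly on the first row. In the second row the exclusion sentence shared by both documents does the work, and it undercuts the protocol's own inclusion sentence.

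**2. The plan's own figures**

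Inputs from Protocol 10.2 and SAP 2.4, with 15 + 15 patients per cohort:

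- Cohort A: null 5%, alternative 18%, continue if at least 1/15, success if at least 4/30.
- Cohort B: null 13.3%, alternative 29%, continue if at least 2/15, success if at least 7/30.

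With a the stage 1 minimum and r the final minimum:

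P(success) = sum over x ≥ a of P(X1 = x) × P(X2 ≥ r − x), where X1 and X2 are Binomial(15, p).

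| | Power | Type I error | Early stop under the null |
|---|---|---|---|
| A computed (stated) | 80.0% (80%) | 5.8% (6%) | 46.3% (46%) |
| B computed (stated) | 80.1% (80.1%) | 9.2% (9.2%) | 38.8% (38.8%) |

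All stated figures reproduce.

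**3. Dropped but not replaced**

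Take three dropped from 30 treated. At the Cohort A threshold the reported ORR is 4/27 = 14.8% instead of 4/30 = 13.3%. At the Cohort B threshold it is 7/27 = 25.9% instead of 7/30 = 23.3%. The go rules are counts of responders, and removing a non-responder leaves the count unchanged, so the type I error stays at 5.8% and 9.2%.

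**4. Dropped and replaced**

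Let c be the share of treated patients who are non-responders, stop before Week 12 for clinical progression, and are dropped and replaced. Of N treated, pN respond and (1 − c)N are evaluable, so the rate in the evaluable set is p/(1 − c). Putting p0/(1 − c) into the formula in step 2:

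| c (assumed) | A: rate | A: type I error | B: rate | B: type I error |
|---|---|---|---|---|
| 0 | 5.00% | 5.8% | 13.30% | 9.2% |
| 5% | 5.26% | 6.8% | 14.00% | 11.3% |
| 10% | 5.56% | 7.9% | 14.78% | 14.0% |
| 15% | 5.88% | 9.3% | 15.65% | 17.4% |
| 20% | 6.25% | 11.0% | 16.63% | 21.6% |

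Solving for a type I error of 10% gives c of about 17% in Cohort A and just above 2% in Cohort B. At c = 20%, the chance of stopping at stage 1 under the null falls from 46.3% to 38.0% (A) and from 38.8% to 26.1% (B).

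**5. Bound if 30 treated were a hard cap**

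The type I error could then not exceed P(X ≥ 4 of 30 at 5%) = 6.1% in A, or P(X ≥ 7 of 30 at 13.3%) = 9.4% in B. The larger figures in step 4 need more treated patients, for example 30/0.8 = 37.5 at c = 20%.

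**The case against.** The strongest reply is that the inflated error rates rest on replacement, which Protocol 8.2 rules out for treated patients outside the safety run-in, and that enrolment is described as up to approximately 30 per cohort. This stands: without replacement, or with a firm cap at 30 treated, neither cohort exceeds its 10% target. It does not settle the matter, because three other places say that non-evaluable patients are replaced.

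Second, the protocol synopsis asks for imaging at discontinuation when a patient stops for anything other than confirmed radiological progression. That will give many clinical progressors a scan, often one showing progression, and so lower c. A gap remains, because the scan is waived if imaging was done in the previous 4 weeks.

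Third, success means only that further research is warranted, in a single-arm phase 1/2 trial. That limits the harm but does not remove the contradiction.

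A reader might infer more than the documents support:

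- That the SAP's word alone removes every early clinical progressor. It does not; those without a scan are removed under both documents.
- That the median survival below 6 months in Protocol 3.3 supports a large c. That figure concerns patients who also progressed on platinum. It is not a rate of unscanned early progression, and it does not describe Cohort B, where the computed inflation is largest. Eligibility also requires ECOG 0 or 1 and excludes rapid progression with clinical deterioration.
- That the null rates are known to refer to all treated patients. Neither document states the denominator behind 5% or 13.3%.

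**Conclusion.** The point holds. SAP 4 and Protocol 10.3 give different rules for the primary ORR set, in current text, and the change is undeclared. The unrestricted wording in the synopsis and SAP 9.5 covers both types of progression, so it conflicts with the SAP's restriction but is not a third rule.

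The direction is clear: dropping near-certain non-responders raises the reported ORR with or without replacement. The effect on type I error is conditional. With replacement, Cohort B passes 10% once c is just above 2%, while Cohort A needs about 17%. Without replacement there is no increase. The value of c is an assumption throughout, so the 11.0% and 21.6% at c = 20% show how far the error could move under that assumption; they do not estimate the trial's actual error rate.

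**What to change.** - Use one definition in SAP 4, Protocol 10.3 and the synopsis: every treated patient who stops before Week 12 for radiological or clinical progression, or who dies before Week 12, is in the set and counts as a non-responder for ORR.
- Exempt these patients from the sentence that excludes anyone without a post-baseline assessment. Deaths need naming because SAP 5 lists death as a separate reason for ending treatment.
- State that these patients are not replaced, and reconcile Protocol 8.2 with Protocol 5.2, SAP 2.2 and SAP 9.1.
- Delete the Cohort A futility sentence in SAP 2.4. Otherwise stage 1 would still leave progressors out, against SAP 4 and SAP 9.5.
- Report ORR in all treated patients as a sensitivity analysis.

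The cost is wording, plus one extra table for the sensitivity analysis. No new data are needed: progression and death are already recorded as reasons for ending treatment (SAP 5). Progression is not split there into radiological and clinical, so the inclusive rule is also the easier one to program. The downside is a slightly lower reported ORR.

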### *Safety Run-In Set*

Safety Run-in Set comprises all patients who receive at least 1 dose of the study treatment or component of the study treatment as part of the safety run-in.

### *Immunologic Analysis Set*

Immunological Analysis Set comprises all patients who receive at least 1 dose of the study treatment or component of the study treatment and have at least one valid post-baseline immunologic assessment available.

## 5. SUBJECT DISPOSITION

Subject disposition will be summarized overall for all subjects who entered the study in a disposition table (i.e., signed the informed consent for the study). In addition, the number of subjects in each population (Safety Analysis Set, Safety Run-in Set, Efficacy Evaluable Analysis Set and Immunologic Analysis Set) and subjects that were removed from a population will be summarized. The number and proportion of subjects who complete the study, as well as those who discontinue the study will be summarized along with the reason for discontinuation.

Primary reason for SNS-301 treatment termination include the following criteria:

- Adverse Event

Sponsor: Sensi Biotherapeutics

Protocol: SNS301-2-2

- Death
- Progression
- Lost to Follow-up
- Non-Compliance with Study Drug
- Physician Decision
- Pregnancy
- Protocol Deviation
- Site Terminated by Sponsor
- Study Terminated by Sponsor
- Withdrawal by Patient
- Other

Primary reason for Pembrolizumab treatment termination include the following criteria:

- Adverse Event
- Death
- Progression
- Lost to Follow-up
- Non-Compliance with Study Drug
- Physician Decision
- Pregnancy
- Protocol Deviation
- Site Terminated by Sponsor
- Study Terminated by Sponsor
- Withdrawal by Patient
- Other

Primary reason for study discontinuation include the following criteria:

- Death
- Lost to Follow-up
- Withdrawal by patient from Study
- Termination of study by Sponsor
- Completed 24 months of therapy
- Other (Disease progression, Unacceptable toxicity as judged by the Principal Investigator, Adverse events, which are dose-limiting toxicities, Withdrawal of consent, Subject is lost to follow-up, Subject non-compliance, Use of another non-protocol anti-cancer treatment, Pregnancy)

Subject disposition data will also be presented in data listings.

If study treatment is definitively discontinued, the patient will remain in the study for long term follow-up post-treatment to be evaluated for survival, including information on subsequent anticancer therapies and progression. In the case where consent for study treatment is withdrawn,

Sponsor: Sensi Biotherapeutics

Protocol: SNS301-2-2

the patient will be encouraged to continue study participation for long term follow-up post-treatment.

## 6. DEMOGRAPHIC AND BASELINE CHARACTERISTICS

### 6.1 Demographics Characteristics

Demographic and baseline characteristics at study entry will be summarized in tables and listings by study cohort and overall.

Number, mean (SD), median, min and max will be provided for these continuous variables:

- Age (years) at time of consent
- Weight (kg)
- Height (cm)
- Body Mass Index (kg/m^2)

Number and percentage of patients will be provided for the following categorical variables:

- Sex
- Child-bearing potential (females)
- Race
- Ethnicity

Patients are allowed to select more than one race to define multiple-race.

### 6.2 Smoking History and Alcohol Use

Smoking history and alcohol use data will be collected at study entry and will be summarized in tables and listings by cohort and overall.

Number and percentage of patients will be provided for the following categorical variables:

- Smoking History (Yes/No)
- Status of Tobacco Use (Current/Former)
- Type (Cigarette, Cigar, Pipe, Smokeless tobacco, Electronic cigarette, Other)
- Tobacco use frequency per day (1- 4, 5-10, 10 - 20, >20, Unknown)
- Alcohol use (Never/Current/Former)
- Number of Alcoholic drinks consumed (never, 1 or 2, 3 or 4, 5 or 6, 7 or 8, 10 or more)

Number, mean (SD), median, min and max will be provided for these continuous variables:

Sponsor: Sensi Biotherapeutics

Protocol: SNS301-2-2

### 6.3 Medical History

Medical History will be collected at the Screening/Baseline visit. will include details regarding the patients overall medical and surgical history as well as detailed information regarding the patient's previous treatment, including systemic treatments, radiation and surgeries, pathology and risk stratification. Medical History will be summarized for the Safety Analysis Set.

The frequency count and percentage of subjects experiencing any medical conditions will be tabulated by system organ classifications (SOC) and preferred term (PT). If a preferred term or system organ class was reported more than once for a subject, the subject would only be counted once in the incidence for that preferred term or system organ class.

Medical history data will also be listed for Safety Analysis Set by patient.

### 6.4 Cancer History

Cancer History will be collected at the Screening/Baseline visit. The following data will be summarized by number and percentage of patients in each category for the Safety Analysis Set.

- Histologic Diagnosis
  - Differentiation (Well, Moderate, Poor, Not Specified)
  - Stage at Screening (Stage I, Stage II, Stage III, Stage IV, Stage IVA, Stage IVB, Stage IVC)
- TNM Staging
  - T Stage (T1, T2, T3, T4)
  - N Stage (N0, N1, N2a, N2b, N2c, N3, NX)
  - M Stage (M0, M1, MX)
- Anatomical Location (Lip, Oral cavity, Oropharynx, Hypopharynx, Nasopharynx, Glottic larynx, Supraglottic larynx, Ethmoid sinus, Maxillary sinus, Salivary gland, Other)

### 6.5 Prior Cancer Therapy

Prior cancer therapy data will be collected at the Screening/Baseline visit.

The following data will be summarized by number and percentage of patients in each category for the Safety Analysis Set.

- Did the subject have any prior Cancer therapy? (Yes/No)
- Was the therapy ongoing at the time of consent? (Yes/No)
- Best Overall Response

Sponsor: Sensi Biotherapeutics

Protocol: SNS301-2-2

- Complete response (CR)
- Partial response (PR)
- Progressive disease (PD)
- Stable disease (SD)
- Unconfirmed Progression (uPD)
- Duration of Response (Weeks) will be summarized as a continuous variable (N, Mean (SD) Median Min Max)

